RESEARCH PROTOCOL

Title	Effect of GLP-1 receptor agonists on trabecular bone score and visceral adiposity in postmenopausal women with type 2 diabetes mellitus.
Principle Investigator/Co- investigators	PI: [name] Co-Investigators: [name], [name], [name], [name], [name], [name], [name] [name], [name]
Abstract	 Postmenopausal women with diabetes mellitus have a higher risk of osteoporotic fractures, with significant associated mortality and morbidity. Osteoporosis is underdiagnosed in diabetes, as the bone mineral density (BMD) as currently measured is often normal despite underlying abnormalities. The trabecular bone score (TBS) is a novel modality to assess bone microarchitecture and accurately assess fracture risk in patients with diabetes. Due to increased co-prevalence of osteoporosis and diabetes mellitus, the potential effects of antidiabetic medications on fracture risk assume importance. Based on findings in animal studies, we hypothesize that GLP-1 receptor agonists increase TBS in postmenopausal women with type 2 diabetes mellitus (T2DM). We propose a prospective non-randomized case-control study by enrolling 48 patients (24 in the GLP group and 24 in the non GLP group). DXA scans, markers of bone formation, and resorption, and selected inflammatory markers will be assessed at baseline, six months and one year. We expect to see a significant improvement in TBS in the GLP group as compared to the non GLP group. We also expect to see a decrease in bone resorption markers, inflammatory mediators, and visceral adiposity and an increase in bone formation markers in the GLP group as compared to the non GLP group.

Purpose Hypothesis: "Administration of GLP-1 receptor agonists will increase TBS in postmenopausal women (age > 55) with T2DM by reducing visceral fat mass and associated production of inflammatory mediators(IL-1, IL-6 and TNF-alpha), leading to a decrease in bone resorption (assessed by measuring C-telopeptide). We further hypothesize that GLP-1 receptor	Background	Osteoporosis is characterized by compromised bone strength and predisposition to fractures. It affects 200 million women worldwide; one in three women over age 50 will suffer an osteoporotic fracture. [1, 2]Osteoporotic hip fractures are expected to increase from 1.6 million to 4.5 million worldwide by 2050. [3] T2DM affects 422 million people worldwide, including about 25% of adults in the United States. Several studies have reported a 20-30% increased risk of osteoporotic fracture with T2DM. Importantly, with increased life expectancy the co- prevalence of T2DM and osteoporosis with resultant fractures, is expected to increase. [4, 5] Typically, osteoporosis is diagnosed by assessing BMD on a DXA scan. T2DM patients often have normal or increased BMD by DXA despite abnormalities of trabecular bone that can lead to increased fracture risk. A TBS can be derived by analyzing pixel gray level variations in DXA image to assess the bone microarchitecture. Higher scores are seen in patients with dense trabecula and lower scores in those with sparse trabeculae. T2DM is known to be associated with low TBS even when BMD is normal. [6] Several T2DM medications can affect bone metabolism. Thiazolidinediones (TZD) are PPAR-y agonists which are used in the treatment of T2DM. They inhibit osteocyte formation and are associated with increased BMD and increased risk of fractures. [7] Sodium glucose co-transporter (SGLT2) canagliflozin has also been associated with increased fractures. [8] GLP-1 receptor agonists have been shown to decrease visceral adiposity, reduce levels of inflammatory markers and improve trabecular bone microarchitecture but their effect on humans has not been assessed. [9] This is the objective of the current proposal.
agonists will decrease sclerostin levels, leading to increased bone	Purpose	"Administration of GLP-1 receptor agonists will increase TBS in postmenopausal women (age > 55) with T2DM by reducing visceral fat mass and associated production of inflammatory mediators(IL-1, IL-6 and TNF-alpha), leading to a decrease in bone resorption (assessed by measuring C-telopeptide). We further hypothesize that GLP-1 receptor

Specific Aim(s)	Aim 1: To test the hypothesis that administration of GLP-1 receptor agonists will increase trabecular bone score in postmenopausal women (age >55 years) with T2DM. Aim 2: To test the hypothesis that administration of GLP-1 receptor agonists will decrease visceral fat mass, and decrease production of inflammatory markers (IL-1, IL-6, TNF-alpha) in postmenopausal women (age>55 years) with T2DM, and that this will be associated with decreased bone resorption (assessed by measuring C-telopeptide). Aim 3: To test the hypothesis that administration of GLP-1 receptor agonists will decrease sclerostin, with an associated increase in bone formation (assessed by measuring osteocalcin and P1NP), in postmenopausal women (age >55 years) with T2DM.
Study Period (inclusive years)	Prospective (June 1, 2019- December 31, 2022)

Study Design	This is a prospective non-randomized study of one year duration. A total of 48 (24 in the GLP group and 24 in the non GLP group) postmenopausal females will be enrolled in the study. This study design will allow us to study the effects of GLP-1 receptor agonists on bone metabolism (formation and resorption); and bone microarchitecture (TBS) and also provide evidence regarding the potential role of visceral adipose tissue in bone metabolism in postmenopausal women with T2DM. All UMMC providers in the division of endocrinology will be briefed about the study and all the participants will be drawn from the UMMC Endocrinee, Family Medicine, and Internal Medicine clinics. The treating providers will have sole discretion in the choice of medications to be used for the management of each patient's type 2 diabetes mellitus. Patients who are enrolled in the study will be placed in the GLP group if they are on GLP-1 receptor agonists (for the treatment of their diabetes mellitus as decided by their endocrine provider) or in the non GLP group if they are not on GLP-1 receptor agonists. Throughout the study, the management of the each patient's T2DM will be according to standard of care as decided by the treating provider, for both the groups. Methodology: Eligible participants will be identified by designated Research
	The treating provider will independently make the decision regarding the treatment of the patient's diabetes mellitus (whether GLP-1 receptor agonist or other medication needs to be started or not), then the treating provider will enquire if the patient is interested in participating in the study.

	If the patient is interested, the treating provider will notify the research personnel who would see the patient promptly in the privacy of the examination room and then explain to the patient about the study in detail (objectives, design, tests involved and follow up, etc.) and seek their consent. Once consent is obtained then the research personnel will enroll the participant to the appropriate group (GLP vs non GLP) based on the medications prescribed by the treating provider. The research personnel will coordinate with radiology to schedule the baseline, 6 months and 1 year DXA scan. We will obtain research blood draws at baseline, 6 months and 1 year utilizing the same venipuncture done for routine clinical labs at these visits.
	the three DXA scan amounting to a total of 30\$ for the entire study. Please see the Schedule of events document for a detailed description of study procedures.
Inclusion Criteria	Criteria that will identify the study population -A diagnosis of Type 2 Diabetes Mellitus -Postmenopausal female -Age >55 years - Hemoglobin A1c between 7 and 10 within 6 months of the first visit.
Exclusion Criteria	List all exclusion criteria* -A diagnosis of Type 1 Diabetes mellitus -History of GLP-1 receptor agonist/DPP4 inhibitor use -eGFR <30 ml/min in the last 3 months -History of pancreatitis -Documented personal or family history of medullary thyroid cancer -Documented history of treatment with anti-osteoporosis agents - Documented secondary osteoporosis -Documented presence of prosthesis or devices in the spine -Unwilling or unable to consent

Number of Participants/	
Records to be reviewed (anticipated)	48
	The primary outcome will be change in TBS from baseline to six months and one year after the initiation of a GLP-1 receptor agonist. TBS will be assessed by DXA scans done at baseline, six months and one year.
	The secondary outcomes are - Change in visceral fat mass (measured by DXA) at 6 and 1 year after starting GLP-1 receptor agonists as compared to baseline.
Outcome Measures	- Change in inflammatory markers and bone resorption markers (as measured by commercial assays) at 6 and 12 months after starting GLP- 1 receptor agonists as compared to baseline.
	- Changes in levels of sclerostin, osteocalcin, and P1NP (as measured by commercial assays) from baseline to six months and one year after starting GLP-1 receptor agonist.
	Statistical methods to assess changes in individual measures and possible correlations among different measures (e.g. TBS, visceral fat mass, and biomarkers) are described below.
Study Endpoints	Outcomes will be assessed at six months and one year and will be compared to baseline values.

	PHI to be accessed: Patient's medical record
	PHI to be collected:
	Name, Address, phone number and email address
	Medical record number
	Date of birth
	Race (African American or Caucasian)
	Duration of menopause (Years and months)
	Duration of T2DM (Years and months)
	Smoker (Yes/No) and duration
	Alcohol use (Yes/No) (Years and months)
	Presence of diabetic retinopathy (Yes/No)
	Presence of diabetic neuropathy (Yes/No)
	History of falls and/or fractures (Yes/No)
	List of anti-hyperglycemic medications
	List of current medications
	Weight
	Height
	BMI
Barta da da da alub	Hip circumference
Protected Health	Waist circumference
Information (PHI)	Blood pressure
	Date of DXA scan
	Visceral adiposity index
	Subcutaneous adiposity
	Lumbar trabecular score
	Hemoglobin A1c (%)
	Low density lipoprotein (LDL)
	High density lipoprotein (HDL)
	Total cholesterol
	Triglycerides
	Microalbuminuria/Creatinine ratio
	Interleukin-1 (IL-1)
	Interleukin-6 (IL-6)
	Tumor necrosis factor-alpha
	C-telopeptide Sclerostin
	PINP
	Osteocalcin.
	RedCap will be utilized to record all study date. Access to study data
	will be restricted to members of the study team.

	Statistical analyses were designed in collaboration with [name], PhD (Statistics).
	Means and standard deviations of baseline, six month and one year TBS values will be reported. Changes in TBS will be analyzed using a linear mixed model contrasting the GLP and non GLP groups.
Statistical Methodology	Means and standard deviations of baseline, and 6 and 12-month values of visceral fat mass, IL-1, IL-6, TNF- α and C-telopeptide levels will be reported. Changes in TBS will be analyzed for any correlation the changes in visceral fat mass, levels of inflammatory mediators and C-telopeptide in the GLP and non GLP groups using linear or logistic regression as appropriate.
	Means and standard deviations of baseline, six month and one-year values of sclerostin, P1NP and osteocalcin will be reported and analyzed for any correlation to the changes in TBS in the GLP and non GLP groups linear or logistic regression as appropriate.
	Power analysis : The primary endpoint is the change in TBS at 6 and 12 months compared to baseline. From prior studies we expect a 10% increase in TBS (corresponding to 0.117 for human TBS) for the GLP group only. With a difference of 0.117 between 24 cases and 24 controls we have power of >0.8 and < 5% probability of type 1 error. The primary motivation for this pilot study is to assess effect sizes to support more accurate power calculations, to be used in an application for extramural funding to conduct a larger, definitive study.

	1) Kanis JA (2007) WHO Technical Report, University of Sheffield, UK: 66.
	2) https://www.iofbonehealth.org/facts-statistics#category-14 as accessed on 4/1/2019.

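### Aims 2 and 3 hypothesise marker-to-marker associations, but every association the plan specifies is with TBS, so these links go unanswered by the analyses as planned

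*Combined protocol and SAP*

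**What the plan says.** **Aims (Specific Aim(s)).** Aim 2 first says that GLP-1 receptor agonists lower visceral fat mass and IL-1, IL-6 and TNF-alpha. It then adds a second hypothesis: "and that this will be associated with decreased bone resorption (assessed by measuring C-telopeptide"). Aim 3 says that the drugs "will decrease sclerostin, with an associated increase in bone formation (assessed by measuring osteocalcin and P1NP"). TBS belongs to Aim 1 and appears in neither of these statements.

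**Outcome Measures.** The section closes by saying that methods for changes in individual measures and "possible correlations among different measures (e.g. TBS, visceral fat mass, and biomarkers) are described below".

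**Statistical Methodology.** Apart from means and standard deviations, three analyses are named:

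- for TBS: "Changes in TBS will be analyzed using a linear mixed model contrasting the GLP and non GLP groups";
- for the Aim 2 markers: "Changes in TBS will be analyzed for any correlation the changes in visceral fat mass, levels of inflammatory mediators and C-telopeptide";
- for the Aim 3 markers: "sclerostin, P1NP and osteocalcin will be reported and analyzed for any correlation to the changes in TBS".

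The second and third are to use linear or logistic regression.

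**The concern.** The hypothesised pathway has two arms. One runs from visceral fat and inflammation to bone resorption, the other from sclerostin to bone formation. The Purpose text describes both in causal terms. Study Design also promises evidence on the role of visceral fat in bone metabolism, which it glosses as formation and resorption and lists separately from TBS. To examine either arm, a fat or inflammatory marker must be set against C-telopeptide, or sclerostin against P1NP and osteocalcin. No such analysis is specified.

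Followed as written, the study would measure every marker at three time points and report how each relates to TBS. It would say nothing on whether the markers move together as the aims propose. If the pairs were chosen only after the data were seen, a reader could not tell a stated hypothesis from a selected finding. The pilot is meant to supply effect sizes for a larger study, and the marker-to-marker slopes are among those it would want.

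**Working it through.** **1. Match each hypothesised link to a planned analysis.**

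| Link in the aims | Analysis in Statistical Methodology |
|---|---|
| Visceral fat with C-telopeptide (Aim 2) | None; each is related to TBS change |
| IL-1, IL-6, TNF-alpha with C-telopeptide (Aim 2) | None; each is related to TBS change |
| Sclerostin with P1NP (Aim 3) | None; each is related to TBS change |
| Sclerostin with osteocalcin (Aim 3) | None; each is related to TBS change |

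Reading the Aim 2 analysis as one multivariable regression does not help. With TBS change as the outcome, its coefficients describe TBS and not the relation of fat or cytokines to C-telopeptide.

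**2. Can the TBS correlations stand in?** Let A and B be the changes in two markers and T the change in TBS. A valid correlation matrix requires

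r_AB = r_AT·r_BT ± √[(1 − r_AT²)(1 − r_BT²)] at the limits.

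The documents give no correlations, so take r_AT = r_BT = r as an assumption:

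- r = 0.2: 0.04 ± 0.96, so -0.92 to +1.00
- r = 0.4: 0.16 ± 0.84, so -0.68 to +1.00
- r = 0.6: 0.36 ± 0.64, so -0.28 to +1.00

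The lower limit stays below zero until r² exceeds 0.5, that is, until r is above about 0.71. The extremes occur only if the partial correlation of A and B given T is exactly -1 or +1. A milder case leads to the same conclusion: at r = 0.4, r_AB = 0.16 + 0.84 × (partial correlation), so partial correlations from -0.5 to +0.5 give r_AB from 0.16 − 0.42 = -0.26 to 0.16 + 0.42 = 0.58. The sign is still open.

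**3. What would direct analysis give?** The sample size is 24 per group, 48 in all. With Fisher's z, the 95% CI is tanh[atanh(r) ± 1.96/√(n − 3)]. For an assumed observed r of 0.4, atanh(0.4) = 0.424:

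- n = 48: 0.424 ± 1.96/√45 = 0.424 ± 0.292, so 0.13 to 0.61
- n = 24: 0.424 ± 1.96/√21 = 0.424 ± 0.428, so about 0.00 to 0.69

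Both sizes are shown because the plan's wording, "will be reported and analyzed for any correlation to the changes in TBS in the GLP and non GLP groups", may mean pooled or within-group analysis. For one unadjusted correlation, two-sided 5% and 80% power, the detectable r is tanh[(1.96 + 0.84)/√(n − 3)]: about 0.39 with 48 women and about 0.55 with 24. All of these figures assume complete pairs.

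**4. The plan's own figure.** The only stated power, above 0.8, concerns a TBS difference of 0.117. No standard deviation is given, so it cannot be reproduced, and nothing here depends on it. The plan states no figure for the marker associations.

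**The case against.** Four points can fairly be made for the plan.

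- **The data will be there.** All markers are measured at baseline, six months and one year, and Outcome Measures shows a general intent to correlate measures that is not confined to pairs with TBS. A reader might infer from the gap that the study cannot answer these parts of Aims 2 and 3. The documents do not support that: the analyses could be run without new data. What remains is that Outcome Measures defers to a section that does not specify them.
- **Aim 3 can be read loosely.** An associated increase may mean only an accompanying one. The Abstract supports this, since it expects group differences marker by marker and mentions no correlation between markers. This stands in part, and Aim 2 is the firmer basis for the point. The loose reading does not complete the plan, however. It would need a comparison of sclerostin, P1NP and osteocalcin between groups, and the group-contrast model is stated for TBS only.
- **The TBS regressions have a purpose.** A reader might conclude that they address the wrong question. They do not: the Purpose says that TBS rises because fat and inflammation fall and resorption decreases, so relating TBS to each marker serves that hypothesis. They are incomplete.
- **It is a small non-randomised pilot.** True, and the added results will be imprecise. That argues for labelling them exploratory. It does not argue for leaving out an association that the aims state.

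**Conclusion.** The point holds as a gap between aims and analyses. The marker-to-marker association in Aim 2, and the less explicit one in Aim 3, are not answered by the analyses as planned. This follows from the text alone. The supporting range of -0.68 to +1.00 rests on an assumed correlation of 0.4 with TBS and serves only to show that the TBS regressions cannot substitute.

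The gap concerns secondary aims. It does not affect the primary TBS comparison and does not make the aims unanswerable. Nor would filling it establish the proposed pathway, because slopes from 48 non-randomised women estimate association and not mechanism.

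The association clauses are also only half of what is missing. The leading clauses of Aims 2 and 3, that the drugs lower fat, inflammatory markers and sclerostin, have no between-group model either.

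**What to change.** In Statistical Methodology, add as exploratory analyses, each adjusted for group:

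1. 12-month change in C-telopeptide regressed on change in visceral fat mass and, in separate models, on change in IL-1, IL-6 and TNF-alpha (four models).
2. 12-month change in P1NP, and in osteocalcin, regressed on change in sclerostin (two models).

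Report slopes with 95% CIs as estimates of association. Keep the TBS regressions as the link to Aim 1.

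A time-ordered version is optional. If it is wanted, relate the upstream change from baseline to six months to the downstream change from six to 12 months. A baseline-to-12-month outcome would overlap the predictor's window and so would not order the steps.

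For the treatment-effect clauses, extend the linear mixed model contrasting the groups to the markers in Aims 2 and 3: visceral fat mass, IL-1, IL-6, TNF-alpha, C-telopeptide, sclerostin, osteocalcin and P1NP.

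**Cost.** A few sentences of statistical text, six exploratory association models, and the same mixed model run on eight further measures (five in Aim 2, three in Aim 3). There are no new visits, samples or participants. The downside is more estimates with wide intervals, so the exploratory label should be explicit.

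### Does a primary TBS outcome timed from GLP-1 start, at two visits, conflict with the planned GLP versus non GLP analysis?

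*Combined protocol and SAP*

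**What the plan says.** In the combined protocol and SAP, Outcome Measures gives the primary outcome as "The primary outcome will be change in TBS from baseline to six months and one year after the initiation of a GLP-1 receptor agonist". A secondary outcome has the same form: "Change in visceral fat mass (measured by DXA) at 6 and 1 year after starting GLP-1 receptor agonists as compared to baseline". Study Endpoints adds: "Outcomes will be assessed at six months and one year and will be compared to baseline values". None of these lines mentions the non GLP group. Outcome Measures ends by saying that the statistical methods for the individual measures are described further down.

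Statistical Methodology then says: "Changes in TBS will be analyzed using a linear mixed model contrasting the GLP and non GLP groups". Its power analysis restates the endpoint as "The primary endpoint is the change in TBS at 6 and 12 months compared to baseline". It expects a 10% rise (0.117) in the GLP group only, and it claims power above 0.8 with under 5% type 1 error for a difference of 0.117 between 24 cases and 24 controls. No visit is attached to that claim. The Abstract also states its expected result as GLP against non GLP.

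Women enter the comparison group under Study Design, "or in the non GLP group if they are not on GLP-1 receptor agonists", and Exclusion Criteria rules out "History of GLP-1 receptor agonist/DPP4 inhibitor use".

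**The concern.** There are two reasons for suspicion.

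- **Time origin.** Taken literally, the primary outcome starts at first use of a drug that half the sample is not taking. It would then be undefined for 24 of the 48 women, and the only comparison left would be change from baseline within the GLP group. That comparison credits the drug with any change that would have happened anyway; the group contrast removes shared change. A team using one could claim an effect where a team using the other finds none.
- **Two visits, one error rate.** The endpoint is set at 6 and 12 months, but there is a single power figure and a single type 1 error figure. No visit, average, joint test, order of testing or adjustment is named. If a significant result at either visit were enough, the error limit would not hold.

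The study is meant to supply an effect size for a larger trial, so an ambiguous primary comparison could carry forward.

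**Working it through.** **1. Are there two rival tests?**

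| Section | What it settles |
|---|---|
| Outcome Measures, Study Endpoints | The variable: change in TBS from baseline, at 6 and 12 months |
| End of Outcome Measures | The methods are left to the later section |
| Statistical Methodology | The comparison: change contrasted between groups |
| Power analysis | The effect: 0.117 between 24 and 24 |
| Abstract | The expected result: GLP against non GLP |

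A change from baseline as the variable and a group contrast as its analysis fit together. No section plans a significance test within one group.

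**2. Is the variable defined for the non GLP women?** Study Design covers enrolled participants without regard to group: "The research personnel will coordinate with radiology to schedule the baseline, 6 months and 1 year DXA scan". Each woman therefore has a baseline scan from which change can be measured. Earlier GLP-1 use is an exclusion, and enrolment follows the prescribing decision. For the GLP women, initiation is thus a loose name for the start of follow-up.

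**3. The plan's power figure.** Inputs from the power analysis: difference 0.117, n = 24 per group, 5% error (taken as two-sided), power above 0.8. No SD is given, so the figure cannot be reproduced. Solving for the largest SD that allows power of 0.80 at one visit:

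SD = 0.117 × √(24/2) / (1.960 + 0.842) = 0.4053 / 2.802 = 0.145 (0.142 with the t distribution).

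At assumed SDs of 0.10, 0.12, 0.15 and 0.20, the normal approximation gives power of 0.98, 0.92, 0.77 and 0.53. The claim is true for SDs up to about 0.14, and the documents do not show it to be wrong.

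**4. Type 1 error under each way of using two visits.**

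- One named visit, the average of both, or one joint test: one test, 5%.
- Success required at both visits, each at 5%: at most 5%.
- Success at either visit, each at 5%: 1 − P(|Z₁| < 1.96 and |Z₂| < 1.96). With independence this is 1 − 0.95² = 0.0975. With correlation it falls:

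| Correlation between the two tests (assumed) | 0 | 0.5 | 0.7 | 0.9 | 0.99 |
|---|---|---|---|---|---|
| Type 1 error | 9.75% | 9.07% | 8.35% | 7.04% | 5.66% |

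Only the last rule breaks the stated limit, and the plan does not state that rule.

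**5. Does the power claim survive the other choices?** Assume 0.117 at both visits, with equal SDs.

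- Average: its variance is SD² × (1 + ρ)/2, which is never above SD², so power is no lower than at one visit.
- Both required: power is at least 1 − 2 × (1 − power at one visit). That is 1 − 2 × 0.018 = 0.964 at SD 0.10 and 1 − 2 × 0.078 = 0.844 at SD 0.12. At the limiting SD of 0.145 it is 0.64 (correlation 0) to 0.75 (correlation 0.9).

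Only the both-visits rule at the larger SDs would take power below 0.8.

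**The case for a change.** The best case for a change is that deferring the methods to a later section does not repair the time origin in Outcome Measures, and that no reading of the document identifies the deciding visit. The protocol states a hypothesis, a power and an error rate, so calling it a pilot does not remove the need for one primary test. The remedy would be a few words, with no extra patients or scans.

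Much of this is true. The initiation wording does not suit the non GLP women. A provider might start the drug later in one of them, since treatment stays at the provider's discretion, but that would not supply the missing definition. The unnamed visit is a real omission.

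The objection does not, however, identify a wrong figure or an unsound analysis. Following Statistical Methodology gives a group contrast of change from a common baseline, which is the comparison the objection itself wants. On the visits, it can only ask that one of several equally valid contrasts be written down. The excess error depends on a permissive rule that the text never adopts. The pilot's purpose is also protected: means and standard deviations of TBS are to be reported at baseline, 6 months and one year, so the material for planning the next study does not depend on which visit decides.

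**Conclusion.** The concern does not hold as a conflict between two primary tests. The plan has one comparison, GLP against non GLP, and both the mixed model and the power statement refer to it. The initiation phrase is a slip of wording that the scheduled baseline scans make harmless. The unnamed deciding visit is missing detail that an analyst would ordinarily fill with one visit, an average or a joint contrast. Each of these keeps type 1 error at 5%.

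The most that could be at stake is an error of about 5.7% to 9.75% instead of 5%, and only under an either-visit rule that the plan does not contain. That range assumes two-sided 5% tests and correlations of 0.99 down to 0, because the documents give no correlation. The power claim can be neither confirmed nor refuted without an SD. The conclusion assumes that the contrast is chosen before outcome data are examined, and that the result is presented as the pilot the plan says it is.

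### The primary TBS contrast compares provider-chosen groups with no confounder adjustment stated; a small pre-specified adjusted contrast should be reported beside it

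*Combined protocol and SAP*

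**What the plan says.** **Allocation (Study Design).** The study is non-randomized. "The treating providers will have sole discretion in the choice of medications" is the rule, and research staff then place each woman by what was prescribed. The provider's decision is described as "whether GLP-1 receptor agonist or other medication needs to be started or not", and it comes before consent and before the baseline DXA is scheduled.

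**Aim 1 (Specific Aims).** "To test the hypothesis that administration of GLP-1 receptor agonists will increase trabecular bone score in postmenopausal women". This is a statement about the effect of the drug.

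**Primary analysis (Statistical Methodology).** "Changes in TBS will be analyzed using a linear mixed model contrasting the GLP and non GLP groups". The section names no covariate, weighting, propensity or matching step. Its regressions relate TBS change to visceral fat, inflammatory markers and bone markers. Those are hypothesised mediators or correlates, so the regressions do not control confounding.

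**Control by design (Inclusion and Exclusion Criteria).** Women must be over 55 and have "Hemoglobin A1c between 7 and 10 within 6 months of the first visit". Earlier GLP-1 receptor agonist or DPP4 inhibitor use, anti-osteoporosis treatment and documented secondary osteoporosis are excluded.

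**Candidate confounders.** The Background says "Several T2DM medications can affect bone metabolism". Of thiazolidinediones it says "They inhibit osteocyte formation and are associated with increased BMD and increased risk of fractures", and it adds "Sodium glucose co-transporter (SGLT2) canagliflozin has also been associated with increased fractures". Neither class is excluded. The Protected Health Information list also collects date of birth, menopause and diabetes duration, BMI, HbA1c, smoking and anti-hyperglycemic drugs. None of these is tied to the model.

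**The concern.** When providers choose the treatment, the two groups may differ in ways that also affect how TBS evolves. Run as written, the contrast estimates the drug effect plus any such difference, so it cannot by itself support Aim 1's causal wording.

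Two features limit the problem. A stable group difference in TBS level cancels when change is analysed, and eligibility narrows some imbalance. What remains is a pre-treatment factor that both differs between groups and predicts TBS change. The sign is open. More use of bone-adverse drugs in the non GLP group would flatter GLP-1 agonists; steering GLP-1 agonists to women with a worse expected bone course would do the opposite.

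The study's stated motivation is to supply effect sizes for a larger study. Confounding would carry into that calculation. Unlike sampling error, it does not show in the confidence interval and does not shrink with more patients.

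**Working it through.** **Inputs from the documents:** 24 v 24; expected difference 0.117; claimed power above 0.8; type 1 error below 5%. **Not in the documents, so assumed:** the SD of TBS change, the imbalance d in one baseline factor (0.5 to 1.0 SD), and its within-group correlation r with TBS change (0.1 to 0.3). The test is taken as a two-sided t test at 5% with 46 df, at one visit, without dropout.

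**1. The plan's power figure.** It cannot be reproduced without an SD. With 24 v 24, 80% power needs a difference of 0.826 SD, so the claim implies an SD of change below about 0.117/0.826 = 0.142. Power for 0.117 is 98% at SD 0.10, 91% at SD 0.12 and 80% at SD 0.142.

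**2. Bias and false positives with no true effect.** Bias = d × r, in SDs of change. The SE is √(2/24) = 0.289 SD and the noncentrality is bias/0.289. For example, 0.5 × 0.3 = 0.15 and 0.15/0.289 = 0.52, which gives 8.0%.

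| r | d = 0.5 | d = 0.8 | d = 1.0 |
|---|---|---|---|
| 0.1 | 5.3% | 5.8% | 6.3% |
| 0.2 | 6.3% | 8.4% | 10.4% |
| 0.3 | 8.0% | 12.9% | 17.4% |

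The biases (0.05 to 0.30 SD) all lie inside the 95% half-width of 0.581 SD, so sampling error is the larger of the two.

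**3. How strong r = 0.3 is.** Suppose 30% of one group and 10% of the other use a drug. The within-group SD of use is √((0.21 + 0.09)/2) = 0.387, and d = 0.20/0.387 = 0.52. Then r = 0.3 means that users' TBS change differs from non-users' by 0.3/0.387 = 0.77 SD, close to the 0.826 SD that gives 80% power. At r = 0.1 the difference is 0.26 SD. So r = 0.3 is a strong-confounder case.

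**4. Power if the bias opposes a true 0.117** (ranges over d).

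| SD of change | No bias | r = 0.1 | r = 0.3 |
|---|---|---|---|
| 0.10 | 98% | 95-97% | 84-93% |
| 0.12 | 91% | 84-88% | 63-80% |
| 0.142 | 80% | 69-75% | 43-63% |

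**5. The form of adjustment depends on the outcome modelled.** Both checks simulate data with no true effect.
- *TBS level, with baseline as an outcome visit:* the 12-month group-by-visit coefficient averaged 0.0182 unadjusted, 0.0182 with the covariate as a main effect, and 0.0000 with covariate by visit (120 datasets). The main effect does nothing here.
- *Change from baseline as the outcome:* the group coefficient fell from 0.265 to 0.016 with a main effect alone (100 datasets, different assumed values). The main effect suffices here.

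**6. Does adjustment improve the estimate?** Simulated mean squared error in SD², over d = 0.5 to 1.0, three covariates. The two halves are separate simulations, so their unadjusted figures differ slightly.

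| r | Unadjusted | Adjusted, confounder in the set | Unadjusted | Adjusted, confounder missed |
|---|---|---|---|---|
| 0.1 | 0.084-0.093 | 0.094-0.112 | 0.086-0.095 | 0.093-0.101 |
| 0.2 | 0.092-0.122 | 0.090-0.107 | 0.093-0.123 | 0.098-0.129 |
| 0.3 | 0.105-0.172 | 0.086-0.103 | 0.108-0.173 | 0.114-0.179 |

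Adjustment wins at r = 0.2 (narrowly at d = 0.5) and at r = 0.3, but only if the set contains the confounder, here measured without error. It loses at r = 0.1, and at every setting if the confounder is missed. With six covariates including the confounder, the range at r = 0.2 is 0.097-0.114, so a larger set gives no reliable gain there.

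**The case against.** The best case against: this is openly a non-randomized pilot, sampling error exceeds every bias illustrated, and the documents support no value of r. The Background links thiazolidinediones and canagliflozin to fractures or BMD, not to TBS change. Nothing shows that BMI or years since menopause predicts TBS change either. At r = 0.1 the error rate is near nominal and adjustment makes the estimate worse. Two or three covariates cannot secure a causal aim.

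Most of this stands, and it rules out several stronger readings that a reader might draw:
- *Covariates must always interact with visit.* The sentence on the primary analysis literally speaks of changes in TBS, and with change as the outcome a main effect does adjust the contrast.
- *The adjusted estimate must be primary.* Its advantage depends on choosing the right covariates and on confounding that is not weak.
- *Baseline visceral fat is a safe covariate.* It comes from a DXA scheduled after the treatment decision, and nothing says that the scan precedes the first dose.
- *There is no matching anywhere in the study.* The recruitment text is broken in the available copy, so the statement is safe only for the analysis section.

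The objection does not remove the omission. Pilot status makes an estimate with undisclosed handling of confounding less useful for planning the next study.

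**Conclusion.** The omission is certain: allocation is by provider choice, and the primary analysis names no adjustment. The harm is possible in either direction, and its size is unknown. Under the assumed values, the false-positive rate runs from 5-6% (r = 0.1) to 8-17% (r = 0.3, a strong confounder). The power figures rest in addition on an SD that the plan does not state.

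A reader might infer that the comparison is shown to be biased, or biased in favour of GLP-1 agonists. The documents support neither. They show only that the contrast as planned cannot separate a drug effect from pre-treatment differences, and that baseline data which might reduce the problem are collected but unused. This should be fixed, at modest cost.

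**What to change.** Pre-specify an adjusted group contrast with two or three covariates fixed before the treatment decision. Examples are years since menopause, pre-treatment BMI, and thiazolidinedione or SGLT2 inhibitor use that predates the decision. A drug started at that same decision is part of the comparator and should not be adjusted for. Leave out post-baseline mediators such as change in visceral fat, and DXA visceral fat itself unless the scan is shown to precede the first dose.

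State the model form. If TBS level is modelled with baseline as an outcome visit, interact the covariates with visit. If change from baseline is the outcome, a main effect suffices for the overall contrast, and interaction is optional for visit-specific effects.

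Report the adjusted and unadjusted contrasts side by side, each with a 95% CI, with a baseline balance table. Word the conclusion as an association with possible residual confounding.

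**Cost.** Mainly SAP text. The data list does not mention drug start dates (the case report form is not in the documents), so they may have to come from the medical record, which the plan already allows staff to access. If covariates explain 20% of group choice and none of the outcome, the SE rises by √(1/0.8) = 1.118, about 12%. Power then falls from 80% to about 71% at SD 0.142, or from 98% to about 94% at SD 0.10. The mean squared error is also higher than unadjusted if confounding is weak or the covariates miss the confounder, which is why the set stays small and both estimates are shown. Only measured confounding is removed.
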